After the training, eligible subjects will be grouped by dojo preference, and randomized 1:1 within each dojo into **Arm 1**: immediate participation in six months of twice-weekly karate classes, or **Arm 2**: usual exercise for six months. After six months, Arm 1 participants may opt to pay for dojo membership and continue classes, and Arm 2 participants will crossover and begin six months of twice-weekly karate classes. Only the Research Coordinator will know which subjects belong to Arm 1 and Arm 2, and she/he will deliver all study-related communication to the subjects.

The karate classes have been specifically designed for individuals with early- to middle-stage PD, focused on incorporating upper and lower limb movements in multiple directions, increasing awareness throughout the body, shifting body weight and rotation, relaxation of the muscles, improving reaction time, using complex repetitive actions to improve coordination, footwork training and centered weight shifts to help with fall prevention, and striking shields for self-defense and stress relief. The PI and study team will provide instruction on PD to all instructors prior to study launch, and will be available and responsive to any questions or concerns throughout the course of the study. The structure of the 6-

month curriculum will be identical at each of the five dojo locations. If a subject misses a class, they may choose to make up a class at one of the other dojo locations.

Every two months, subjects in both Arms will receive an online link to report their attendance at classes, indicate whether their PD medication regimen has changed (as a potential confounder), and complete the IPAQ, HADS, and PDQ-8. In addition, the survey will contain the Physical Activity Group Environment Questionnaire (PAGEQ) to measure camaraderie, and Patient Global Impression of Change (PGIC) for the subject's global impression of change. The online survey will be delivered through a secure online database called Research Electronic Data Capture (REDCap). The purpose of the online surveys is to track adherence to karate classes, adherence to other walking/moderate/vigorous activity, quality of life, anxiety, depression, global impression of change, and group cohesion.

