After six months, participants in both arms will have a second in-person study visit in which the pre-intervention assessments will be re-administered (MDS-UPDRS, TUG, IPAQ, MoCA, PDQ-8, HADS, SDMT, DST, and instrumented gait analysis), along with the PAGEQ and PGIC. The PI and co-investigators performing the MDS-UPDRS will be blinded to subjects' assignments. Following completion of all assessments, without the blinded raters present, all participants will be reminded to continue completing the bimonthly online surveys over the upcoming six months, and the Research Coordinator will explain to Arm 2 on the crossing over process into the active intervention (karate classes), and participants will be provided with information on the timing and location of classes. Individuals in Arm 1 will be asked to stay and participate in a brief focus group on the first six months of classes; PI and co-investigators will not be present during the focus group in order to preserve the blind. Subjects will be prompted to share their thoughts on how the intervention impacted their overall wellbeing, balance, and mindfulness; whether the intervention achieved their expectations; whether they intend to continue, and what feedback they would like to provide.

After twelve months, participants in both arms will have a third in-person study visit* in which the pre-intervention assessments will be re-administered (medication regimen, MDS-UPDRS, TUG, IPAQ, MoCA, PDQ-8, HADS, SDMT, DST, and instrumented gait analysis), along with the PAGEQ and PGIC. The PI and co-investigators performing the MDS-UPDRS will remain blinded to subjects' assignments. Following completion of all assessments, all subjects will be asked to stay and participate in a brief focus group to reflect on the entire study. Given the number of subjects, study staff may divide the group into Arm 1 and Arm 2 participants, with concurrently running focus groups in separate rooms to ensure all participants have the opportunity to speak; again, PI and co-investigators performing ratings will not be present to preserve blinding. The script for both groups will be identical.

*Covid-19 Procedures for 12 month study visits:

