Our sample size calculation (see table below) is based on the results from the pilot study with the primary outcome being change in TUG. We powered our original study based on existing literature, in which the mean TUG score for individuals with PD is 14.8 seconds with standard deviation of 5.8 seconds, and minimum clinically important difference values for the TUG ranged from 2 seconds to 5 seconds in various studies.^{1,17} However, our pilot cohort had a pre-intervention baseline mean TUG of 9.6 seconds, standard deviation of 2.1. As per the tables below, if our new cohort has a similar baseline mean TUG, we would need 12 individuals in each arm to detect a difference of 2 seconds with 90% power, however this may not be plausible (i.e., 9 seconds may be close to the limit of how quickly anyone can complete the TUG task). If, however, participants have a more modest baseline to start, which may be expected when recruiting more broadly than at a tertiary referral center, we yield the second half of the table below. Here, we are extrapolating a baseline mean TUG of 12.5 with SD 4.0 (between our pilot data and the existing literature); with 19 individuals per arm, we would be 90% powered to detect a 3s difference between pre- and post-intervention TUG.

If we assume up to 25% attrition in this group of older adults with a chronic neurodegenerative disease, particularly in a longitudinal study over six months, we need to enroll 52 individuals (26 per arm) to yield a total of 40 completing the study.

Baseline mean TUG	Baseline SD TUG	Minimum clinically Important difference	Power	Sample size per arm
9.6	2.1	2s	.9	12
			.8	9
9.6	2.1	3s	.9	6
			.8	4
9.6	2.1	4s	.9	3
			.8	3
9.6	2.1	5s	.9	2
			.8	2
12.5	4.0	2s	.9	43
			.8	32

12.5	4.0	3s	.9	19
			.8	14
12.5	4.0	4s	.9	11
			.8	8
12.5	4.0	5s	.9	7
			.8	6

II.b. Gender of Subjects

There will be no exclusion of subjects based on gender.

II.c. Age of Subjects

Subjects will be 30-90 years of age.

II.d. Racial and Ethnic Origin

There will be no exclusion of subjects based on racial or ethnic characteristics. However, subjects must be fluent in English to participate in the karate classes, as that is the language of instruction, and due to the general lack of appropriately translated neurological and neuropsychological assessments and appropriate normative comparison samples. These factors are critical for accurate administration, scoring, and interpretation of neurological and neuropsychological test data.

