Once all subjects have completed the assessments above, the baseline visit will continue with a one-time, in-person, group training highlighting current research on the benefits of exercise for PD. This training will be delivered by the study team in collaboration with an experienced physical therapist familiar with evidence-based recommendations for safe and effective exercise programs for individuals with early to middle stage PD. Participants will leave the training with printed, publicly available materials on exercise for PD as references.

Depending on participant and study staff availability and schedules, multiple pre-intervention study visits will be held to accommodate all participants.

Intervention

Each karate class will follow a structured curriculum, as shown in Appendix 1, with complexity of movements and movement patterns increasing over the six-month study period. Classes will take place twice weekly, and subjects will be required to attend their assigned class time/location, or make up missed classes at another dojo location, if possible. Each class will last approximately 45-60 minutes. Attendance will be recorded in hard copy by the instructors at each class, with recordings only of the subject's name, not linked to their unique study ID; the attendance log will be shared with the Research Coordinator following the final class. The study staff will be available by phone to answer questions and to support participants and instructors should any questions about protocol or PD safety arise.

Bimonthly online survey

Using the survey functionality of the HIPAA-secure, password-protected REDCap electronic database, all participants in both arms will automatically receive a personalized email every two months directing them to indicate how frequently they have attended karate classes (Arm 1) or how frequently they have engaged in exercise as discussed at the initial study visit (Arm 2), whether their PD medication regimen has changed (as a potential confounder), and complete the IPAQ, HADS, and PDQ-8. In addition, the survey will contain the Physical Activity Group Environment Questionnaire (PAGEQ) to measure camaraderie, and Patient Global Impression of Change (PGIC) for the subject's global impression of change.

Six-month study visit

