Data will be exported from REDCap in de-identified format for statistical analysis, with all PHI stripped from the dataset prior to analysis by statisticians. We will summarize categorical variables by frequencies and percentages and will assess continuous variables for normality, summarized by mean/standard deviation, or median/interquartile range. We will report the basic descriptive statistics of the cohort, including baseline demographics, TUG, MDS-UPDRS, HADS, PDQ-8, IPAQ, SDMT, MoCa, and DST. We will report on attendance, defined as the percentage of classes attended, in each arm once active. We will analyze the change in TUG, MDS-UPDRS, HADS, PDQ-8, IPAQ, SDMT, DST, MoCa, and PAGEQ respectively, from baseline to six months, comparing Arm 1 and 2 (active vs. control), and again at twelve months to determine whether longer participation yields additional benefits, using paired *t*-tests or nonparametric Wilcoxon sign rank tests, as appropriate. We will report on the percentage of subjects endorsing each of the 7 PGIC response options at six and twelve months, between Arms, respectively. We will report the descriptive statistics concerning whether subjects’ individual predefined goal for the class was achieved (binary outcome), and will present de-identified qualitative comments noted in the feedback at the study visit focus groups. We will report descriptive statistics on continued interest and likelihood of recommending the program to someone else with PD. We will analyze descriptive statistics on continued involvement in karate/martial arts, and will again report the percentage of subjects endorsing each PGIC response option.

The qualitative data from the study visit focus groups will be audio-recorded and transcribed, with all identifying information stripped from the transcripts. Once transcribed, the audio recordings will be destroyed. The qualitative data will be analyzed using a grounded theory approach to identify pertinent themes, with data stored as password-protected files behind the Rush firewall, accessible only to study staff.

All video footage will be the sole property of the PI. Videos will have identifying information (i.e. image of patient’s face, first name). Video files will be stored and password-protected behind the Rush and the Columbia firewalls. The video along with the data collected from the focus groups and karate classes may be used as part of the dissemination of the study results and for educational purposes.

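### PDQ-8, HADS and IPAQ are collected every two months, but the month-2 and month-4 values have no planned analysis, and a participant without a month-6 value drops out of the arm comparison

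*Combined protocol and SAP*

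**What the plan says.** **Collection.** Section I.c schedules the survey for both arms: "Every two months, subjects in both Arms will receive an online link to report their attendance at classes". Participants also "complete the IPAQ, HADS, and PDQ-8" in it. Section III, under the bimonthly online survey, confirms that "all participants in both arms will automatically receive a personalized email every two months". Section I.c gives the purpose as tracking adherence and other activity, and also "quality of life, anxiety, depression, global impression of change, and group cohesion". At the six-month visit participants are reminded to "continue completing the bimonthly online surveys over the upcoming six months".

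**Analysis.** Section III.b is the only analysis text. It takes change in each scale "from baseline to six months, comparing Arm 1 and 2 (active vs. control), and again at twelve months", using paired t-tests or "nonparametric Wilcoxon sign rank tests, as appropriate". PGIC is also reported at six and twelve months only. The text available for review contains no analysis of months 2, 4, 8 or 10, no repeated-measures model, no as-randomised analysis set and no rule for missing values.

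**Attrition.** Section II.a: "If we assume up to 25% attrition in this group of older adults". It enrols 52 (26 per arm) on that basis.

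**The concern.** A change score to month 6 needs a month-6 value. Someone who answers at months 2 and 4 and then leaves has given two post-baseline readings on each scale, yet contributes nothing to the arm comparison as specified.

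Two things are at stake. The smaller is precision. The larger is bias. Participants know whether they are attending karate, and the burden differs between arms (twice-weekly classes against usual exercise), so reasons for leaving may differ too. If karate participants whose scores worsen are the ones who leave, those who stay look better than the arm as randomised. The interim scores are the information that a likelihood-based model would use to correct this.

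**Working it through.** **The plan's own figures.** Section II.a gives 19 per arm for a 3 s difference, SD 4.0 and 90% power. Alpha is not stated; two-sided 0.05 is assumed. The one-sample formula gives (4.0 × (1.960 + 1.282) / 3)² = 18.7, so 19. Then 19 / 0.75 = 25.3, so 26 per arm and 52 in total. Completers: 52 × 0.75 = 39, against the stated 40. These figures rest on TUG, which is not in the survey, so this point leaves them unchanged.

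**Records without a planned use.** Surveys at months 2, 4, 6, 8, 10 and 12 give 6 × 52 = 312 scheduled post-baseline values per scale before drop-out. The analysis uses months 6 and 12, leaving 4 × 52 = 208 unused. At 25% attrition, 0.25 × 52 = 13 people could lack a month-6 value.

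**Precision of the month-6 arm difference.** Assumptions, none from the documents: unit SD; correlation 0.5 to 0.8, either equal at all times (compound symmetry) or AR(1) per two-month step; 25% monotone loss in each arm, leaving 19.5 per arm at month 6. Let n2, n4 and n6 be the numbers per arm still observed at months 2, 4 and 6. Let v1, v2 and v3 be the residual variances of the month-6 score given baseline; baseline and month 2; and baseline, months 2 and 4.

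- Complete-case ANCOVA, per arm: v1 / n6.
- Repeated-measures model, per arm: v3 / n6 + (v2 − v3) / n4 + (v1 − v2) / n2.

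Even drop-out gives n2 = 23.83, n4 = 21.67 and n6 = 19.5.

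- Compound symmetry 0.5: v1 = 0.750, v2 = 0.667, v3 = 0.625. Model: 0.03205 + 0.00192 + 0.00350 = 0.03747. ANCOVA: 0.03846. Ratio 1.026.
- AR(1) 0.8: v1 = 0.738, v2 = 0.590, v3 = 0.360. Model: 0.01846 + 0.01063 + 0.00619 = 0.03528. ANCOVA: 0.03784. Ratio 1.073.

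These are the ends of the range.

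| Timing of loss | Extra information over complete-case ANCOVA |
|---|---|
| All before month 2 | 0% |
| Even over the three intervals | 3–7% |
| All after month 4 (n2 = n4 = 26) | 4–15% |

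With even loss this equals 19.5 × 1.026 = 20.0 to 19.5 × 1.073 = 20.9 completers per arm. The standard error falls by 1 − 1/√1.026 = 1.3% to 1 − 1/√1.073 = 3.4%.

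**Bias, as an illustration.** Suppose no true effect, higher scores worse (as for PDQ-8), 25% loss in each arm, random in the control arm. In the karate arm the quarter with the worst month-4 change leaves. The mean standardised month-4 change of those who stay is −0.318 / 0.75 = −0.424. Under compound symmetry with correlation r, the month-6 change regresses on the month-4 change with slope 1/2, and the month-4 change has SD √(2(1 − r)). The false benefit in a completer change-score comparison is:

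- r = 0.6: 0.5 × 0.424 × 0.894 = 0.19 SD.
- r = 0.8: 0.5 × 0.424 × 0.632 = 0.13 SD.

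Under AR(1) with step correlation ρ, the slope is (1 + ρ)/2 and the SD is √(2(1 − ρ²)). This gives 0.8 × 0.424 × 1.131 = 0.38 SD at 0.6 and 0.9 × 0.424 × 0.849 = 0.32 SD at 0.8.

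A milder pattern is 40% loss above the median month-4 change and 10% below. Stayers then average 0.798 × (0.30 − 0.45) / 0.75 = −0.160. Under compound symmetry the false benefit is 0.5 × 0.160 × 0.894 = 0.07 SD at 0.6 and 0.05 SD at 0.8.

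In each case loss depends on baseline and month-4 scores. The model conditions on both, so it removes this bias if its assumptions hold.

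**The case against.** The strongest reply is that the gap is one of omission and its measurable cost is small. Most of that stands.

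- A reader might infer that the plan discards interim data or restricts itself to completers. It says neither. The accurate statement is that no analysis is specified and that a paired change needs both values.
- A reader might infer that everyone who misses the six-month visit is lost. A two-monthly survey also falls due at month 6 and could supply all three scales. The plan does not say which value counts.
- The gain for the month-6 difference is a few percent, and zero if people leave early. The comparator, complete-case ANCOVA, is not the plan's test. Against a between-arm change score the gain looks larger (16–37% under compound symmetry 0.5–0.8, even loss). Most of that is baseline adjustment: ANCOVA alone gains 2/(1 + r) − 1, which is 33% at 0.5 and 11% at 0.8.
- No document reports or predicts differential drop-out, and people who leave may also stop answering surveys. The bias figures show what could happen; they do not forecast it.
- Using a paired test to compare two independent arms is a separate matter that affects every outcome.

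None of this gives the month-2 and month-4 values a planned use. The better method needs only data already scheduled for collection.

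**Conclusion.** The point holds as a worthwhile improvement to the analysis of secondary and exploratory outcomes. The precision gain is about 3–7% with even drop-out (0% to about 15% across the timings considered). It rests on assumed correlations of 0.5–0.8, 26 per arm and 25% loss. The better reason to change is protection against bias when leaving depends on earlier observed scores.

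Three stronger readings are not supported:

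- **That the standard error falls by 26–32%.** That compares the average over months 2–6 with month 6 alone, which is a different quantity. Averaging the three visits in completers alone already gives 21–27%.
- **That quality of life is a named aim with the clearest pilot signal.** The aims name mobility, balance, camaraderie and overall wellbeing, and the hypothesis on wellbeing uses PGIC. HADS is listed as exploratory. The pilot PDQ-8 change (25.3 to 19.3, p < 0.01) came from 15 people without controls. Significant cognitive gains are reported beside it without p-values, so the signals cannot be ranked.
- **That the primary result or sample size is affected.** TUG is not in the survey.

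**What to change.** In III.b, for PDQ-8, HADS and IPAQ, replace the paired tests for the month-6 arm comparison with a likelihood-based repeated-measures model:

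- Outcomes at months 2, 4 and 6, all before Arm 2 crosses over.
- Terms for baseline score, arm, month, arm-by-month and dojo, with a small-sample degrees-of-freedom correction such as Kenward–Roger.
- All randomised participants, as assigned.
- Skewed scores, such as IPAQ, transformed before modelling.
- At month 6, the visit value, or the online survey value if the visit is missed. I.c lists IPAQ at the six-month visit but the visit description in III does not, so state where it is collected.
- The month-6 arm difference as the estimate, with the months 2–6 average as supportive only.
- Months 8–12 described separately, because both arms may then be doing karate.

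The cost is a few sentences in the plan and a little more analysis work, with no new data or visits. The model relies on loss depending on observed scores. The data cannot confirm this, so the plan should state the assumption.

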
Based on these promising results from the pilot, we are therefore proposing the next step in this line of research, namely, a randomized, controlled trial of a structured karate intervention for individuals with PD. Individuals will receive a one-time, in-person training in best practices for exercise in PD. Due to both the capacity of the karate classes and the scientific approach to detecting changes in PD, subjects will be randomly assigned into either **Arm 1**: immediate participation in the karate class or **Arm 2**: participation in usual exercise for six months followed by karate classes for six months. For participants in **Arm 1**, following the first six months of classes, subjects may choose to continue their participation in karate and in the study, though this will require paying membership fees at the *dojo* (karate studio). For participants in **Arm 2**, following the first six months of usual exercise, participants will then begin 6 months of twice-weekly classes. We will conduct in-person assessments of motor function, attention, and cognition at baseline, six months, and twelve months. We will conduct online assessments of adherence to exercise program, quality of life, anxiety, depression, global impression of change, and group cohesion via bimonthly online surveys. We will assess feasibility with measurement of attendance at each class, and sustainability with the rate of attendance among the participants beyond their first six months of classes.

We hypothesize: 1) Subjects will show improved mobility after 6-months of twice weekly karate classes, as measured by change in Timed Up & Go (TUG)¹ and MDS-UPDRS motor subscore; 2) The majority of subjects will report a positive change from baseline in their overall wellbeing, as measured by a response of “very much improved”, “much improved” or “minimally improved” on the Patient Global Impression of Change Scale (PGIC)² following 6 months of classes; 3) Feasibility will be high, as measured by $\geq 75\%$ attendance rate and a response of “yes” to either “Would you recommend this program to someone else with PD?” or “If available, would you continue to participate in this or a similar karate class?”

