Remaining 12-month data assessments will be administered electronically. Treatment, HADS, IPAQ, PDQ-8, Attendance and Camaraderie, Global Impression of Change, & Post-Intervention questionnaires will be administered over the phone and/or video call. UPDRS will be administered over video call. Cognitive test DST will be administered over the phone. Necessary visual components for the cognitive tests SDMT and MoCA will be emailed to participants to complete and return, and the remainder of these assessments will be administered over the phone. Study team will directly enter all data into REDCap.

Expanding on work begun in the pilot study, the PI and research team will collaborate with an associate professor of Cinema and Television Arts from Columbia College Chicago, IL to develop a documentary to educate others about karate as an interactive form of exercise and its potential benefits on the

symptoms and quality of life of people with PD. To capture the group's journey, portions of the karate classes and study visit focus groups will be videotaped. For a more in-depth look, 2-10 subjects will be followed during the entire study and interviewed to provide a personal narrative of their experiences with the karate classes and living with PD. The interviews will be videotaped.

We will recruit 52 individuals with PD diagnosed by a neurologist, ages 30-90, living in Chicago, and with Hoehn & Yahr (HY) stage 1 (unilateral symptoms, no balance issues), stage 2 (bilateral symptoms, no balance issues), or stage 3 (bilateral symptoms, some postural or balance involvement). Subjects must be able to ambulate independently (i.e., they must not require the use of an assistive device or a care partner to ambulate).

II. Characteristics of the Research Population

II.a. Number of Subjects

Total Number of Subjects: 52; 26 in Arm 1, 26 in Arm 2, assuming up to 25% drop-out.

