Subjects will then meet with a study team member to complete the TUG (see description below) . Subjects will meet with another study team member to complete the MoCA, DST, and SDMT (cognitive testing). Next, the subject will meet with the PI or another study team member in a private room for the motor portion of the MDS-UPDRS to test bradykinesia, tremor, rigidity, and postural stability.

Subjects will then proceed with the instrumented gait, functional mobility and balance analysis. The use of body wearable inertial motion sensors is a relatively new paradigm in gait, functional mobility and balance analysis. These portable systems allow less costly, less time consuming and noninvasive testing in natural environments compared to traditional marker based approaches (which are conducted in gait laboratories). Gait and functional mobility variables including sit to stand and turn to sit measures using this technology correlate highly with those obtained from traditional optical marker based motion analysis and forceplate approaches.

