As noted above, due to the Covid-19 outbreak, remaining 12-month data assessments will be administered electronically for participants. Treatment, HADS, IPAQ, PDQ-8, Attendance and Camaraderie, Global Impression of Change, & Post-Intervention questionnaires will be administered over the phone and/or video call. UPDRS will be administered over video call. Cognitive test DST will be administered over the phone. Necessary visual components for the cognitive tests SDMT and MoCA will be emailed to participants to complete and return, and the remainder of these assessments will be administered over the phone. Study team will directly enter all data into REDCap.

Documentary

Portions of the karate classes and 12-month study visit, and potential in-depth interviews, will be videotaped by the Columbia filmmakers using personal equipment. Subjects may choose to not participate in the documentary project which means subjects will not participate in the in-depth video interviews, and they will not be included in individual or group video shots during the focus groups and karate classes.

Assessments: Subjects who agree to be part of the study and sign the Informed Consent Form will be asked to complete a series of assessments to determine their current neurological status and overall wellbeing. There is no known risk associated with participation in these assessments, and they are a part of routine clinical care for these conditions. These tests are typically experienced as interesting to subjects. Administration of these assessments may take up to 60 minutes per subject at the pre-intervention study visit, 6-month study visit, and 12-month study visit. Administration of the bimonthly

online survey assessments may take up to 20 minutes. All or some of the following assessments and self-report measures may be administered but are not limited to:

- *Demographic/disease questionnaire*: This brief, one-page questionnaire will ask for the subject's name, age, gender, race, ethnicity, PD duration in years, prior exposure to karate or martial arts classes, baseline activity level, and number of falls in the past 12 months. There will be one open-ended question asking, "What do you hope to achieve in this class?"

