- *Hospital Anxiety and Depression Scale (HADS)*: Brief, 14-item highly validated scale for measuring anxiety (7 items) and depression (7 items), where scores of >8 for either anxiety or depression indicate probable symptoms.³ The HADS was selected due to its use in prior peer mentoring studies and strong psychometric profile
- *Modified Unified Parkinson's Disease Rating Scale (MDS-UPDRS)*: The motor subscale will be conducted by the PI or study staff, assessing rigidity, resting/postural/intention tremor,

bradykinesia, gait, and balance.

- *Montreal Cognitive Assessment (MoCa)*: a screening instrument designed to help health professionals detect mild cognitive dysfunction. It assesses numerous cognitive domains: attention and concentration, executive functions, memory, language, visuoconstructional skills, conceptual thinking, calculations, and orientation.
- *Patient Global Impression of Change (PGIC)*: This single-item rating scale asks subjects to rate their overall response to the intervention using a 7-point rating scale, with the options of “very much improved”, “much improved”, “minimally improved”, “no change”, “minimally worse”, “much worse” and “very much worse”. Recommendations for assessing importance of this scale include reporting the percentages of subjects endorsing each of the 7 response options.
- *Physical Activity Group Environment Questionnaire (PAGEQ)*: a measure of group cohesion used in sports psychology. This conceptual model of cohesion is a modified version of the GEQ (Group Environment Questionnaire). PAGEQ is divided into two levels of perceptions: an individual’s perspective of a group as a whole (collective) and an individual’s attraction to a group (personal). These two levels are further defined by social and task aspects. All these components are categorized into four constructs: Group Integration-Social (GI-S), Group Integration-Task (GI-T), Individual Attractions to the Group-Social (ATG-S), and Individual Attractions to the Group-Task (ATG-T).
- *Parkinson’s Disease Questionnaire- Short Form (PDQ-8)*: A validated and shortened version of the PDQ-39, with 8 items each representing one domain of the PDQ-39, also with a summary index score standardized to a scale of 0-100, with higher scores signifying worse quality of life; this scale is recommended for use in PD by the Movement Disorder Society.

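### Remote twelve-month visits score the MDS-UPDRS motor exam by video and list no TUG, yet the twelve-month analysis allows for neither

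*Combined protocol and SAP*

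**What the plan says.** The hypotheses, set out before section I.b, begin with mobility: "Subjects will show improved mobility after 6-months of twice weekly karate classes, as measured by change in Timed Up & Go" and the "MDS-UPDRS motor subscore". The sample size in section II.a is built on change in TUG.

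Under Pre-Intervention Study Visit in section III, participants meet the examiner in a private room for the "motor portion of the MDS-UPDRS to test bradykinesia, tremor, rigidity, and postural stability". The list of assessments says: "The motor subscale will be conducted by the PI or study staff, assessing rigidity, resting/postural/intention tremor"; it goes on to bradykinesia, gait and balance. The TUG uses a pre-measured 3 m course, timed with a stopwatch by a team member. The six-month visit is in person and repeats both measures. As first planned, so does the twelve-month visit (section I.c).

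The Covid-19 text changes the later visits. Section I.c states: "Remaining 12-month data assessments will be administered electronically". The Twelve-month study visit part of section III repeats this. Both places move questionnaires and the DST to phone or video, email the visual parts of the SDMT and MoCA, and state: "UPDRS will be administered over video call". Neither mentions the TUG or instrumented gait.

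Section III.b analyses change in TUG, MDS-UPDRS and other scales from baseline to six months, Arm 1 against Arm 2, "and again at twelve months to determine whether longer participation yields additional benefits". It names paired t-tests or signed-rank tests. It does not mention visit mode, unscored motor items or missing TUG.

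**The concern.** Data collection was amended for the pandemic and the analysis was not. A twelve-month motor score obtained by video would be set against hands-on scores from baseline and six months, although the plan does not say which items count or how a total is formed when some cannot be rated. Because only the remaining visits changed, month 12 may contain both modes.

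This matters most for Arm 2. It starts karate after month 6, so month 12 is its only motor assessment after karate. A within-person change has no concurrent control to absorb a change in how the scale is given. For the TUG, a remote visit simply yields no value. If the handling rule is chosen after the data are seen, the twelve-month result can depend on that choice.

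**Working it through.** **1. What is measured at each visit**

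| Visit | MDS-UPDRS motor | TUG |
|---|---|---|
| Baseline | in person, includes rigidity and postural stability | in person |
| Six months | in person | in person |
| Twelve months, before the switch | in person | in person |
| Twelve months, remaining visits | video | not listed |

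The documents do not themselves say that rigidity and postural stability cannot be scored by video. That is an inference from these being hands-on manoeuvres. No substitute or modified score is defined.

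**2. Which comparisons are exposed**

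- Six months, Arm 1 against Arm 2: every value is in person. Not exposed.
- Arm 2, before against after karate: the later value is at month 12. Exposed.
- Arm 1, later follow-up: the month-12 value may be remote. Exposed.
- Month 12, Arm 1 against Arm 2: let p1 and p2 be the remote shares and d the average shift per remote visit, taken as equal in both arms. The shift in the difference is (p1 − p2) × d, which is zero when p1 = p2. The documents give neither share.

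**3. MDS-UPDRS: what can be said about size**

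The sign of d depends on a rule the plan does not give. If unscored items are in effect summed as zero, the total falls and reads as improvement. If a complete total is required, the participant drops out of the analysis. If items are prorated, imputed or carried forward, the shift may be small or go either way.

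For the summed-as-zero case only, and with inputs that are all assumed (mean motor score 25; the two domains contribute 5% to 20% of it; 20% to 50% of visits remote):

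- Fall per remote visit: 25 × 0.05 = 1.25 points, to 25 × 0.20 = 5 points.
- Shift in mean within-person change: 1.25 × 0.2 = 0.25 points, to 5 × 0.5 = 2.5 points.

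The true remote share could lie outside 20% to 50%. Classes were anticipated to end in December 2019 (Screening Phone Call, section III), so many visits may already have been done in person. This range illustrates the mechanism and is not an estimate.

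**4. TUG: reproducing the plan's figure, then removing remote pairs**

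The plan states 19 per arm for a 3 s pre/post difference, SD 4.0, 90% power. No alpha is stated; two-sided 0.05 is assumed.

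- n = (SD × (z₀.₉₇₅ + z₀.₉₀) / difference)² = (4.0 × (1.960 + 1.282) / 3)² = 18.7, rounded up to 19. The same formula matches all 16 rows of the table.
- Attrition: 19 / (1 − 0.25) = 25.3, rounded up to 26 per arm, 52 in total. This agrees with the plan. (52 × 0.75 = 39, against the stated 40.)

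The table is therefore a within-person calculation, and for Arm 2 the after-karate value falls at month 12. Each remote visit removes one pair. Taking 20 completers in Arm 2 (half of the plan's 40) and assumed remote shares, power = Φ(3 / (4.0/√n) − 1.960):

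| Remote share | Pairs left | Power |
|---|---|---|
| 0% | 20 | 92% |
| 10% | 18 | 89% |
| 25% | 15 | 83% |
| 50% | 10 | 66% |
| 75% | 5 | 39% |

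With a t reference distribution the values at 0%, 25% and 50% are 89%, 77% and 56%. Like the plan, this uses the baseline SD as the SD of change.

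**The case against.** The switch to remote visits was forced, and nobody should ask for it to be reversed. More importantly, a reader might infer that the test of hypothesis 1 as a whole is compromised, or that neither of its measures can be compared with baseline. The documents do not support that. The randomised comparison in section III.b runs from baseline to six months, and both visits are in person. Month 12 is given a different purpose, namely whether longer participation adds benefit. For the TUG, any value that exists was obtained in person and is comparable; the problem is absent values.

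A reader might also infer a bias towards karate at month 12. That is not shown either. Both arms follow the same visit schedule and were randomised within dojo, so a common mode shift would largely cancel between arms. Section III.b is silent on unscored items and does not direct that they be counted as zero. The absence of instrumented gait adds little, since the protocol treats it as exploratory and optional.

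All of this stands and limits the reach of the point. It does not remove the gap: within-person change has no such cancellation, and the plan prespecifies nothing for the remote visits it introduces.

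**Conclusion.** The point holds within limits. As written, the plan would compare a video motor score with hands-on scores at month 12, and would analyse twelve-month TUG without acknowledging that remote visits supply none. The results affected are Arm 2's change from before to after karate and the twelve-month follow-up. Mode shifts the month-12 contrast between arms only if remote shares differ, and the six-month randomised contrast is not affected.

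The size and direction of any MDS-UPDRS shift cannot be determined from the documents. For the TUG the loss is one pair per remote Arm 2 visit; the power figures rest on the assumed alpha, completer number and remote shares. This should be corrected, but it does not threaten the main comparison.

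**What to change.** In section III.b, with matching sentences in both Covid-19 paragraphs:

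1. For every twelve-month MDS-UPDRS comparison, use a reduced motor score built from the items that can be scored by video. Use the same item set at baseline, six and twelve months for all participants, whatever their visit mode. Keep the full motor score for baseline to six months.
2. Record visit mode and repeat the twelve-month analysis in in-person visits only, as a sensitivity analysis. Report the remote share by arm.
3. State that twelve-month TUG comes only from in-person visits, and base the hypothesis 1 conclusion on the randomised six-month comparison.

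The cost is a few sentences and one data field; no visit or procedure is added. There are three downsides. The month-12 motor score leaves out two domains. The in-person subset may be small and consists of those seen before the switch. Re-summing needs item-level scores from all visits, and the documents do not say these were kept, so the sponsor must confirm it.
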